**IV. Protocol**

Among Veteran smokers with chronic moderate to severe pain, a pain intensity  $\geq 4$  for 3 or more months, we are proposing a randomized comparative effectiveness trial to compare the effectiveness of a telephone-based smoking cessation intervention including CBI for pain to a standard telephone-based smoking cessation intervention. The goals of the study are: 1) Evaluate the impact of **smoking cessation plus CBI (SMK-CBI)** on cigarette abstinence rates among Veterans with chronic pain at 6 and 12-months compared to **standard smoking cessation counseling (SMK-STD)**; 2) Evaluate the impact of **SMK-CBI** on pain intensity and pain interference among Veterans at 6- and 12-months compared to **SMK-STD**; 3) Assess whether change in self-efficacy and pain-related anxiety mediate the impact of **SMK-CBI** on smoking cessation in Veterans with pain at 6- and 12-months compared to **SMK-STD**.

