## V. Outcomes:

Participants will be surveyed three times: enrollment, 6-months post-intervention and 12-months post-intervention using VA RED Cap to collect these data. Baseline survey will assess demographics, smoking history, nicotine dependence, global self-efficacy to quit smoking, depression, pain intensity and other covariates related to pain and smoking, via telephone. Follow-up surveys will be administered at 6-months and 12 months post-intervention. The follow-up surveys will assess smoking status, pain intensity, use of intervention materials (e.g., NRT, PASS activity booklet), and intervention acceptability (e.g., intervention appropriateness, suitability, effectiveness, and convenience). Participants will be compensated \$25 per completed follow-up survey. We will abide by the patient's preference since many patients may be reluctant to send their sensitive bank information or provide it over the phone for this telephone-based study.

Saliva samples will be collected from participants who report not smoking in the last 7 days (7-day point prevalence) in order to biochemically validate their self-reported smoking status. This process has been shown to improve the validity of self-reported smoking cessation. Samples will be collected at next clinic visit following the telephone interview. Saliva samples will measure cotinine levels using NicAlert dipsticks with a standard cut point of 16 ng/ml to determine abstinence. Participants will receive \$10 incentive for providing each saliva sample.

Counseling session fidelity will be assessed using audio-taped recordings of sessions. We aim to record approximately 20% of sessions (all sessions in the first 3 months of the study and then one week every 2 months for the remainder of the study). Investigators will rate 10% of the sessions to ensure protocol fidelity and lack of drift of information from the SMK-CBI to SMK-STD over time.

**Outcome 1: Prolonged abstinence:** In keeping with the SNRT recommendations for measuring abstinence, we will use prolonged abstinence as our main outcome and allow for a grace period around quit date. During the 6- and 12-month follow-ups, patients will be asked about prolonged abstinence, "In the past 6 months, have

you smoked at least a part of a cigarette on each of 7 consecutive days?" and "In the past 6 months, have you smoked any cigarettes in each of 2 consecutive weeks?"

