### **Analyses**

**Hypothesis 1.1:** Prolonged abstinence rates will be significantly higher among Veterans in the SMK-CBI group compared to those in the SMK-STD group.

**Hypothesis 1.2:** The 7-day point prevalence abstinence rates will be significantly higher among Veterans in the SMK-CBI group compared to those in the SMK-STD group.

Rates of cigarette abstinence (prolonged abstinence) will be assessed at 6- and 12-month follow-up. Abstinence will be measured as a dichotomous variable that indicates whether patients have been abstinent or not. The same analysis approach will be used to test both prolonged and 7-day point prevalence abstinence rates. Self-report of abstinence will be validated with cotinine saliva testing.

We will use logistic regression to test for a between-group difference in abstinence rates at 6 months. This logistic regression model can be written as:  $\text{Logit}(\pi_i) = \beta_0 + \text{SMK-CBI}_i * \beta_1$ , where  $\pi_i$  represents the probability that patient  $i$  has abstained from smoking at the 6-month follow-up. In this model, SMK-CBI $_i$  is the intervention group indicator; therefore,  $\beta_1$  represents the log-odds ratio of smoking abstinence in the SMK-CBI group as compared to the SMK-STD group. For each of the abstinence outcomes, we will formally evaluate the intervention effect by testing that  $\beta_1$  differs from zero and report the odds ratio ( $\exp(\beta_1)$ ) and 95% CI of the odds ratio. An odds ratio significantly greater than 1.0 provides evidence that SMK-CBI group patients have higher prolonged abstinence rates. The model will also include stratification variables (gender) as recommended in the CPMP guidelines.

Sustainability, or longer term effects of the intervention, will be examined by comparing abstinence rates between groups at 12 months. We will model change in abstinence rates at baseline, 6, and 12 months using generalized linear models with a logit link fit with generalized estimating equations. The regression coefficients from this model have essentially the same interpretation as those from a cross-sectional regression analysis (e.g. logistic regression) but are more appropriate as they properly incorporate the within-subject correlation that is inherent in the longitudinal structure of the data. The model will be fit using the SAS procedure GENMOD (SAS Institute, Cary, NC).

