If there is a significant intervention effect on smoking cessation (i.e., if  $\beta_1$  is significantly different from zero in the first model above in Hypothesis 1.1), then we also plan to examine whether change in self-efficacy and pain-related anxiety mediate the impact of the intervention. This aim can be addressed under the general framework of mediation. We propose to conduct this mediation analysis using the MacArthur approach, a modification of the traditional Baron & Kenny criteria, developed for use specifically in randomized clinical trials. By the MacArthur definition, the potential mediator must be evident during or post-treatment; therefore, for example, the change in patient self-efficacy measures between baseline and 6-months will be considered as potential mediators. The outcome will be patients' abstinence at 12-months. We will first fit a model to examine the correlation between the mediator (C) and the SMK-CBI group:  $C = \gamma_0 + \gamma_1 * \text{SMK-CBI}$ . We also fit a model that examines the relationship between the mediator and the probability of abstinence (p):  $\text{logit}(p) = \beta_0 + \text{SMK-CBI} * \beta_1 + C * \beta_2 + C * \text{SMK-CBI} * \beta_3$ . Improvements in patient self-efficacy or pain-related anxiety will be considered to account for improvements in abstinence rates if there is evidence that  $\gamma_1$  is not equal to zero, and if either  $\beta_2$  or  $\beta_3$  are not equal to zero.

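### Goal 3 promises mediation at 6 and 12 months, but only 12-month abstinence is analysed, and that analysis is opened by the 6-month test under a rule that requires no 12-month effect

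*Combined protocol and SAP*

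**What the plan says.** - **Objective.** Section IV (Protocol), goal 3: "Assess whether change in self-efficacy and pain-related anxiety mediate the impact of" the combined intervention "on smoking cessation in Veterans with pain at 6- and 12-months compared to" standard counseling.
- **Schedule.** Section V (Outcomes): "Participants will be surveyed three times: enrollment, 6-months post-intervention and 12-months post-intervention". No mediator measurement at the counseling sessions is described.
- **Survey content.** The baseline list in section V includes "nicotine dependence, global self-efficacy to quit smoking, depression, pain intensity and other covariates related to pain and smoking". Pain-related anxiety is not named there, and the listed follow-up content names neither mediator.
- **Mediation outcome.** Section VI, Hypothesis 3.1: "The outcome will be patients' abstinence at 12-months". The mediator, given by way of example, is the change in self-efficacy from baseline to 6 months.
- **Gate.** Same section: "If there is a significant intervention effect on smoking cessation", defined as a significant β1 in the first Hypothesis 1.1 model. That model is set out under Hypotheses 1.1 and 1.2: "We will use logistic regression to test for a between-group difference in abstinence rates at 6 months". The 12-month comparison is a separate longitudinal (GEE) analysis of sustainability.
- **Decision rule.** The mediator is taken to explain the gain in abstinence if γ1 (group to mediator) is nonzero and either β2 (mediator to 12-month abstinence) or β3 (its interaction with group) is nonzero.

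**The concern.** There are two mismatches of time point.

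The first is between the objective and the analysis. Goal 3 names 6 months, but no analysis of 6-month abstinence follows. The first post-baseline mediator value comes from the same survey as 6-month abstinence, so the mediator would not precede the outcome. Veterans who have already quit may report more confidence because they quit.

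The second is between the gate and the outcome. A significant 6-month effect decides whether 12-month mediation is examined, and nothing in the decision rule then checks that a 12-month effect exists. If the effect fades, the rule can attribute to a mediator a 12-month improvement that the trial did not show. If the effect emerges late, the mechanism is never looked at. One of the trial's three goals depends on this step.

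**Working it through.** The plan gives no figure to reproduce. It states no abstinence rates, alpha, power, allocation ratio or correlation. The time points can be traced through the text. The simulation only illustrates how often the gate and the 12-month result would part.

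**Step 1: trace the time points**

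| Element | Time point | Where |
|---|---|---|
| Objective | 6 and 12 months | IV, goal 3 |
| Earliest post-baseline mediator value | 6-month survey | V, survey schedule |
| Mediator in the model | baseline to 6 months | VI, Hypothesis 3.1 |
| Outcome in the model | 12 months | VI, Hypothesis 3.1 |
| Gate | 6 months | VI, Hypotheses 1.1 and 3.1 |
| 12-month effect required by the decision rule | none | VI, Hypothesis 3.1 |

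The prolonged-abstinence questions look back 6 months. At the 6-month survey, the outcome window therefore closes when the mediator is first re-measured. At the 12-month survey, the window begins about when the mediator was measured, so the order is right for that outcome.

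**Step 2: inputs for the illustration**

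- Sample size. The recruitment paragraph in section 6 gives 371 and 100 without saying whether the 100 is additional. Upper case: 371 + 100 = 471, and 471 / 2 ≈ 235 per arm with no losses. Lower case: 371 in all with 80% retained, 371 × 0.8 / 2 ≈ 148 per arm. The 80% is an assumption; the missing-data section expects dropout but gives no rate.
- Assumed: 1:1 allocation, two-sided 5% tests, 10% abstinence in SMK-STD, and a correlation of 0.6 between the latent normal variables behind each person's 6- and 12-month abstinence.
- Test at each time, with n per arm and p̄ the pooled proportion: z = (p_CBI − p_STD) / √(2 p̄(1 − p̄) / n), significant if |z| > 1.96. This stands in for the logistic test of β1, without the gender term.
- 20,000 simulated trials per scenario.

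**Step 3: results**

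| Scenario (SMK-CBI vs SMK-STD) | Per arm | Gate opens | 12 months significant | Gate open, 12 months not significant | Gate shut, 12 months significant |
|---|---|---|---|---|---|
| Effect gone: 18% vs 10% at 6 months, 10% vs 10% at 12 | 235 | 71% | 5% | 68% | 2% |
| Same | 148 | 52% | 5% | 49% | 2% |
| Late effect: 14% vs 10% at 6 months, 18% vs 10% at 12 | 235 | 27% | 71% | 4% | 48% |
| Same | 148 | 19% | 52% | 6% | 39% |

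**Step 4: what the figures do not measure**

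The simulation contains no mediator. Declaring mediation also needs γ1 and either β2 or β3 to be nonzero, and no rate for that has been calculated.

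**Step 5: check on the replacement rule**

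If the new condition were only that the 12-month estimate lies on the side of SMK-CBI, it would be met in about 47% of trials with no 12-month effect (10% in both arms, 235 per arm). The condition therefore has to be significance, not direction.

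**The case against.** **The 6-month half could still be answered.** A reader might infer from the schedule that no data could address it. The documents do not support that. The 6-month survey falls after the 10 to 12 weeks of counseling, so a baseline-to-6-month change meets the plan's own timing criterion, which accepts a mediator seen during treatment or after it. It could be modelled against 6-month abstinence, including the 7-day measure. What stands is that the plan specifies no such analysis, and that it would be a concurrent association.

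**The 12-month outcome is well chosen.** This is right. A mediator taken at 6 months comes before the 12-month look-back window. The fault lies in the gate and the decision rule.

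**Testing mechanism only after the main test succeeds is a usual hierarchy.** The 6-month test comes first in the plan and 12 months is treated as sustainability, so calling the gate simply wrong would be a judgement. But the plan gives no reason for tying a 12-month mechanism to a 6-month result, and its decision rule has no 12-month condition to make up for this.

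**The percentages overstate the harm.** A reader might take 68% as the chance of a false mechanism claim. It is not, for the reason in step 4. An indirect effect can also exist at 12 months without a significant total effect. Nor is disagreement under identical effects at both times (about 16% in each direction, 32% in all, at 235 per arm) evidence against the gate: it mostly reflects two correlated tests, each with about 71% power.

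**Conclusion.** The concern holds in a limited form. Two facts rest on the text alone. Goal 3 names a 6-month mediation question for which no analysis is specified and for which the schedule allows only a concurrent association. The 12-month mediation analysis is opened by the 6-month effect, under a decision rule that requires no 12-month effect.

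The size depends on assumptions that the documents do not supply. Under those listed, the gate opens without a significant 12-month effect in about 49-68% of trials if the effect has gone, and stays shut despite one in about 39-48% if the effect is late. Both are rates of gate disagreement. The change is worth making before the analysis because it is cheap and concerns a stated goal; the trial's main abstinence comparison is not affected.

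**What to change.** 1. **Section IV, goal 3.** Restrict the mediation objective to 12-month abstinence, or keep 6 months and label that analysis as concurrent and exploratory. Hypothesis 3.1 names no time point, so its wording needs no restriction.
2. **Section VI, Hypothesis 3.1.** Remove the 6-month gate and run the 12-month mediation analysis whatever the 6-month result. Report the 12-month odds ratio with its 95% CI beside it. State that a mediator accounts for a gain in abstinence only when the 12-month odds ratio is significantly greater than 1; otherwise report the mediation result as exploratory.
3. **Section V.** List self-efficacy and pain-related anxiety, with their instruments, in both the baseline and the 6-month survey content. The analysis depends on them, and the follow-up list names neither.

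Cost: wording in the protocol and statistical section. Goal 3 becomes slightly narrower, and one analysis is always run. No extra participants or visits are needed. If the mediator items are not already in the surveys, adding them lengthens those surveys somewhat.

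### The Aim 3 mediation rule tests no direction and estimates no indirect effect; for self-efficacy it also cannot tell a mechanism from a consequence of having quit

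*Combined protocol and SAP*

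**What the plan says.** Section IV gives as the third of three study goals: "Assess whether change in self-efficacy and pain-related anxiety mediate the impact of" SMK-CBI on smoking cessation. The method is under Hypothesis 3.1 in the Statistical Protocol: "We propose to conduct this mediation analysis using the MacArthur approach".

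- **Gate.** The analysis runs only if the arm coefficient is significant in the Hypothesis 1.1 model, which concerns the probability that a patient "has abstained from smoking at the 6-month follow-up".
- **Timing.** By way of example, "the change in patient self-efficacy measures between baseline and 6-months will be considered as potential mediators". Then: "The outcome will be patients' abstinence at 12-months".
- **Models.** C = γ0 + γ1·arm, and logit(p) = β0 + β1·arm + β2·C + β3·C·arm. Neither contains 6-month abstinence.
- **Rule.** "Improvements in patient self-efficacy or pain-related anxiety will be considered to account for improvements in abstinence rates if there is evidence that" γ1 differs from zero and at least one of β2 and β3 does. No sign, product, indirect effect or interval is specified.
- **Measurement.** Section V schedules surveys at enrolment and at 6 and 12 months post-intervention. The baseline list includes "global self-efficacy to quit smoking". For follow-up, "The follow-up surveys will assess smoking status, pain intensity, use of intervention materials" and acceptability; neither mediator is named.
- **Quit dates.** Table 1 places the quit date in session 1 (SMK-STD) or session 2 (SMK-CBI) of a five-session programme lasting 10–12 weeks.

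**The concern.** There are two separate problems.

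1. **Direction and size (both mediators).** The plan would conclude that improvement in a mediator explains improvement in abstinence, but it tests only that coefficients are not zero. The favourable direction differs by mediator (self-efficacy up, pain-related anxiety down) and is written for neither. The result is a yes or no, without an estimate of how much of the effect passes through the mediator.

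2. **Order in time (self-efficacy only).** The change score ends at the survey that records 6-month abstinence, months after quit dates are set. Having quit can plausibly raise self-efficacy to quit. Six-month abstinence also predicts 12-month abstinence, so it can produce an association between C and the outcome when C does nothing. The gate requires a declared arm difference in 6-month abstinence, so this route is in play whenever the analysis runs. I make no such argument for pain-related anxiety.

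At stake is whether a path in the wrong direction, or a consequence of quitting, is reported as the way SMK-CBI works.

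**Working it through.** The documents state no power or error figure for Aim 3, so there is none to reproduce.

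**Algebra of the rule.** On the log-odds scale the indirect effect is γ1·β2 in the SMK-STD arm and γ1·(β2 + β3) in the SMK-CBI arm.

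- γ1 = −0.4, β2 = 0.6, β3 = 0: product −0.4 × 0.6 = −0.24. Both conditions hold, but the path runs against SMK-CBI. With assumed intercepts (mediator 0.3, β0 = −2, β1 = 0.9) the natural indirect effect on 12-month abstinence probability is −0.045.
- γ1 = 0.4, β2 = 0.6, β3 = −0.6: SMK-CBI product 0.4 × 0 = 0, yet the rule can be met.
- γ1 = −0.4, β2 = −0.6: product +0.24 from two wrong signs, so a positive product alone is not enough.

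**Simulation inputs.** N = 371 + 100 = 471 (Research Plan), about 235 per arm with 1:1 allocation assumed; 188 = 80% of 235 for 20% loss. Two-sided 0.05 is assumed. Also assumed: 6-month abstinence 20% (or 22%) vs 12%; 12-month abstinence by 6-month status 75%/3%, varied to 50/3, 90/3, 75/6 and 50/6. There were 2,000 trials per cell, of which 1,093–1,676 passed the gate (Monte Carlo SE up to 1.5 points). All rates below are among gated trials.

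**Consequence of quitting.** C = N(0,1) + s × (abstinent at 6 months) + d × arm, and C has no effect on abstinence. Percentage meeting the plan's rule, range over settings:

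| Direct arm effect d (SD) | s = 0.5 SD | s = 1 SD | s = 2 SD |
|---|---|---|---|
| 0 | 1.8–5.1 | 9.4–17.7 | 36.0–47.3 |
| 0.1 | 8.3–18.1 | 29.0–53.2 | 70.9–80.8 |
| 0.2 | 16.8–41.6 | 51.0–84.4 | 91.0–96.4 |
| 0.3 | 22.5–49.9 | 58.6–97.1 | 94.5–99.8 |

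Adding 6-month abstinence to the 12-month model brings this to 0.3–4.2% at d = 0 and 2.4–8.9% at d = 0.1–0.3. For comparison, with s = 0 and d = 0.3 the rule is met in 6.4–7.8%. Two independent 5% tests, either sufficing, would give 1 − 0.95² = 9.75%.

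Runs with other assumptions (371 or 471 in total, 60%/5% persistence, d = 0) agree. At 10% vs 20% quitting the rule is met in 2%, 9–12%, 24–30% and 40–46% for s = 0.5, 1, 1.5 and 2. At 10% vs 30% it is met in 25–37%, 60–74% and 82–93% for s = 1, 1.5 and 2.

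**Wrong-direction path.** SMK-CBI lowers the mediator by 0.1–0.3 SD, the mediator has OR 1.3–1.8 per SD, and intercepts are set to keep 20% vs 12%. The rule is met in 2.0–58.8% if the path acts only through 6-month status and 4.3–83.8% if it also acts later. Of the trials meeting the rule, 79–100% had a negative product.

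**Remedies.** Claim required the bootstrap interval in the SMK-CBI arm to lie on the beneficial side (300 gated trials, 300 resamples, 20% vs 12%, 75/3; SE up to 2.9 points):

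| Truth | Signed interval (%) | Signed interval, 6-month abstinence added (%) |
|---|---|---|
| No mediation, d = 0, s = 0.5 / 1 / 2 | 5.3 / 14.7 / 35.3 | 0 / 0.7 / 1.7 |
| No mediation, d = 0.3, s = 0.5 / 1 / 2 | 59.3 / 97.0 / 99.3 | 2.0 / 4.7 / 4.0 |
| Wrong direction (−0.3 SD, OR 1.8) | 0 | 0 |
| Genuine (+0.3 SD), via 6-month status only, OR 1.5 / 1.8 | 46.3 / 68.0 | 4.0 / 3.3 |
| Genuine (+0.3 SD), also acting later, OR 1.5 / 1.8 | 74.3 / 91.3 | 31.3 / 49.0 |

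The signed interval cures the first problem but not the second. Adjustment removes the second but also removes genuine mediation that runs through early quitting.

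**The case against.** **The rule's subject is improvements, so a worsened mediator would not be reported.** This shows the intent. But what triggers the claim is the set of coefficient tests, and the sign of β2 or β3 is still unspecified. At best the direction is left to judgement at reporting. The missing indirect effect stands either way: γ1, β2 and β3 would be available, but not their combination or its uncertainty.

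**The wrong-direction case is contrived.** SMK-CBI must harm a helpful mediator and still raise abstinence. That is fair as to likelihood. The quoted rates also slightly overstate wrong-direction results, since not every qualifying trial had a negative product.

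**The time-order problem is one of design.** Surveys fall only at enrolment, 6 and 12 months, so SAP wording cannot place the mediator before quitting. True; wording can only limit the claim. The adjusted model discriminates poorly: 3–4% for genuine early mediation against 0–4.7% for none. That is why it should not be a veto.

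**Every input is assumed and the results run from 2% to nearly 100%.** Correct. With a 0.5 SD shift and no direct arm effect the second problem is negligible.

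**A named framework is cited.** Its sources cannot be checked here, so this point concerns only the rule as written. The log-odds product is one choice of scale.

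**The follow-up list is evidently not exhaustive.** It also omits pain interference, which is an outcome. That weakens any inference that the mediators are not collected, but it is worth confirming.

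**Conclusion.** The concern holds, and the plan should be changed. That the rule has no sign condition, no indirect effect and no 6-month abstinence term is clear from the text and needs no assumption. The size is less certain, because the documents give no abstinence rates, persistence, mediator shifts or path strengths.

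Under the assumed inputs, false mediation from reverse ordering is negligible for a 0.5 SD shift with no direct arm effect. It becomes material at 1 SD, and more so if SMK-CBI also moves self-efficacy directly. How often a wrong-direction path would pass depends heavily on its strength. The consequence is confined to Aim 3, which is conditional and secondary.

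**What to change.** In the Hypothesis 3.1 text:

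1. For each mediator, report γ1·β2 (SMK-STD) and γ1·(β2 + β3) (SMK-CBI) on the log-odds scale with bootstrap 95% intervals. Name in advance which one the claim rests on.
2. Claim mediation only if γ1 is in the beneficial direction (self-efficacy up, pain-related anxiety down) and the named interval excludes zero on the beneficial side. Both conditions are needed.
3. Alongside, report a sensitivity model that adds 6-month abstinence, using the same abstinence measure as the 12-month outcome. Name that measure; the text says only abstinence.
4. Do not use the sensitivity model as a veto. If the result holds only without it, say that the data cannot separate mediation through early quitting from a consequence of quitting, and do not present an established mechanism.
5. State that both mediators are measured at baseline and 6 months, and reconcile this with the survey content in Section V.

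**Cost.** SAP wording and a little extra analysis, if both mediators are already in the 6-month survey. If the Section V list is complete, they must be added, which cannot be done once those surveys have been held. The conclusions will be more cautious. The adjusted model conditions on a post-randomisation variable and can hide genuine early mediation (68% to 3% in the example where it runs wholly that way), so it can serve only as a sensitivity analysis.

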**6. Research Plan:**

**Study methods with proactive recruitment:** Potentially eligible patients will be identified by administrative data pull of pain scores equal to or greater than 4 and current tobacco use. We will oversample women Veterans to increase the diversity. Eligible patients will be sent the following components: Introductory letter: A letter from [name] to introduce the study, make an appeal to the patient to quit smoking, and informs them that they will be called to complete a telephone survey unless they call a toll-free number to refuse participation; Informational Consent Document: A document providing all the information for informed consent into the study and will be sent along with introductory letter and that describes the study.

**Other recruitment methods:** Recruitment will also occur via flyers posted in patient care areas, referrals by providers, and self-referrals from Clinicaltrials.gov at VACHS and VA Central Western Massachusetts Healthcare System (VACWM), and with the monthly pain recruitment table at West Haven and Newington. The anticipated goal for this VACHS study is to recruit 371 veterans, and VACWM will look to recruit 100 Veterans.

Approximately seven days after the mailing, Veterans who have not opted out will receive a phone call from a research assistant (RA) to further assess inclusion criteria, obtain informed consent (if interested), and conduct the baseline survey. Eligible patients must be Veterans enrolled at VACHS or VACWM with current tobacco use, willingness to make a quit attempt in the next 30 days, significant pain defined as  $\geq 4$  on the pain intensity portion of the BPI, and report that their current pain has been present for 3 months or more. Veterans with any of the following will be excluded: active diagnosis of psychosis or dementia in their medical records, Non-english speaking, refusal to provide informed consent, severely impaired hearing or speech, lack of telephone access, enrollment in another research study that might affect the main outcomes of this study, or terminal illness. Participants enrolled into PASS will have a research alert noted in their medical record.

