**Hypothesis 2.1:** Veterans in the SMK-CBI will report significantly lower usual pain intensity and pain interference compared to the SMK-STD group.

We will use linear mixed effects models procedure for analyzing repeated measures data with fixed and random effects to evaluate study group assignment effects on our continuous and repeated outcomes (pain intensity and pain interference). The Mixed Models procedure is designed for unbalanced repeated measures with missing data, allowing for intra-participant serial correlation and unequal variance and covariance structure across time. It provides tests of the overall between-participant effects, repeated measures (time) effects, tests of fixed and random effects, and analysis of reduced models that can provide detailed tests of specific pattern of results. A repeated measures analysis of variance in the Mixed Models procedure takes into consideration differences that may emerge over time; we will use this procedure to test for a significant effect of the two treatments on the primary outcome measure, time, and the interactions between time and each of the two treatments. Random effects will also be included to account for intra-participant correlation of repeated measures. Additionally, the model will include the stratification variables. We plan to estimate the parameters in the model using the SAS procedure MIXED (SAS Version 9.2, Cary, NC).

**Hypothesis 3.1:** The relationship between pain-related anxiety intervention and smoking cessation will be mediated by self-efficacy and pain-related anxiety.

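### Aim 3 tests two mediators through equations that hold only one, so a mediator with no effect of its own can be credited when the two are correlated

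*Combined protocol and SAP*

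**What the plan says.** The third goal in IV. Protocol, and Hypothesis 3.1 in VI. Statistical Protocol, concern two mediators. The hypothesis states that the effect on smoking cessation "will be mediated by self-efficacy and pain-related anxiety".

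The analysis paragraph under Hypothesis 3.1 applies only if the intervention effect on abstinence is significant. It then sets out two steps.

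- Step 1: "We will first fit a model to examine the correlation between the mediator (C) and the SMK-CBI group", written as C = γ0 + γ1·SMK-CBI.
- Step 2: a logistic model for abstinence with arm, C and the C-by-arm product, with coefficients β1, β2 and β3.

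On timing, "the change in patient self-efficacy measures between baseline and 6-months will be considered as potential mediators" (given as an example), and "The outcome will be patients' abstinence at 12-months".

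The decision rule is: "Improvements in patient self-efficacy or pain-related anxiety will be considered to account for improvements in abstinence rates if there is evidence that" γ1 is non-zero and at least one of β2 and β3 is non-zero. There is no equation with both mediators, no causal order between them, and no statement of what to conclude if both pass.

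**The concern.** C is a single variable and the rule is worded for one mediator or the other, so the natural reading is one pair of models per mediator. The text does not say this outright, but the equations as written allow no other reading.

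Both candidates are changes measured in the same people after the same five-call programme, and the hypothesis itself supposes that SMK-CBI works through both. Correlation between them is therefore likely. Randomisation protects the step 1 comparison. It does not protect the step 2 slope, because mediators are not randomised. When the other mediator is left out, the slope for the tested one absorbs part of its effect.

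At stake is the interpretation of mechanism: a report could present pain-related anxiety as a mechanism when only self-efficacy acts on abstinence, or the reverse.

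**Working it through.** **Plan's own figure.** There is none. The documents give no power, error rate or effect size for Aim 3, so nothing can be reproduced.

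**Inputs from the documents.** The two equations and the decision rule are as above. On numbers: "The anticipated goal for this VACHS study is to recruit 371 veterans, and VACWM will look to recruit 100 Veterans" (6. Research Plan). That gives 371 + 100 = 471; 371 alone was also run.

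**Assumed inputs.** Equal arms; two-sided 5% tests; about 20% abstinence; both mediators shifted by 0.25 SD; log odds ratio b = 0.4 to 0.6 per SD for the active mediator and zero for the other; within-arm correlation ρ from 0 to 0.6.

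**Why the slope is distorted.** Within arm, the regression of the active on the inert mediator (both in SD units) has slope ρ. The inert mediator's slope when fitted alone is therefore roughly ρ·b:
- ρ = 0.3: 0.12 to 0.18
- ρ = 0.5: 0.20 to 0.30
- ρ = 0.6: 0.24 to 0.36

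**The γ1 condition.** The standard error of the arm difference is √(1/235 + 1/236) = 0.092 SD, so z = 0.25/0.092 = 2.71. Power is Φ(2.71 − 1.96) = Φ(0.75) ≈ 77%. This caps the chance that either mediator is credited.

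**Full written rule by simulation (γ1, and β2 or β3 with the interaction in the model), N=471.**

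| ρ | Inert mediator credited |
|---|---|
| 0 | 6-7% |
| 0.3 | 10-16% |
| 0.5 | 21-36% |
| 0.6 | 26-44% |

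Each range runs over b = 0.4 to 0.6. Separate repeats with 1,500 trials per setting agreed to within about five points (for example 17-36% and 20-31% at ρ = 0.5). At N=371 the figures were 8-11%, 13-23% and 18-32% at ρ = 0.3, 0.5 and 0.6. The 6-7% at ρ = 0 is not due to correlation. Accepting either β2 or β3 contributes to it, and that is a separate matter.

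**Both mediators in one model, no interactions, γ1 still required.** The inert slope is significant in 5-6% of trials. Multiplying by 0.77 gives about 4-5%, and simulation gives about 3-5%. The true mediator is credited in about 60-77%.

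**Sensitivity to the assumptions (N=471, 2,000 trials per setting, 0.4 SD shift, 12% abstinence for a control participant at zero on the active mediator).**

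| Setting, full rule | ρ=0 | 0.3 | 0.5 | 0.7 |
|---|---|---|---|---|
| b = 0.7 | 9% | 20% | 44% | 69% |
| b = 0.4 | 7% | 12% | 18% | 30% |
| b = 0.7, inert shift only ρ × 0.4 SD | – | 6% | 25% | 61% |

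With b = 0.7 and both mediators plus both interactions in one model, the inert mediator is credited in about 7-9% at every ρ. Power for the true mediator falls from about 95% to 86% at ρ = 0.5 and from 94% to 72% at ρ = 0.7.

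**Price in precision without interactions.** Standard errors rise by 1/√(1 − ρ²): 1.05 at 0.3, 1.15 at 0.5 and 1.25 at 0.6.

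**The case against.** Four points can be made on the other side.

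1. *Mediation runs only after a significant abstinence effect.* This stands as a limit on the figures, which are not conditional on that step. If the active mediator were the only path, the implied total log odds ratio would be 0.25 × 0.4 = 0.10 to 0.25 × 0.6 = 0.15, and the arm effect would be significant in only about 7-10% of trials. A direct effect or larger shifts would open the step more often. The weakness in the rule remains whenever the analysis is run.

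2. *The documents do not promise to separate the pathways.* This also stands. A reader might infer that Aim 3 exists to say which mediator carries the effect. The stated goal is only to assess whether the two mediate. The concern is that the rule credits each mediator singly, not that a declared aim of separation is missed.

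3. *A joint model is not neutral.* This stands, and it shapes the remedy. If one mediator acts through the other, the joint model removes the upstream mediator's path. In a simulated serial chain, the genuine upstream mediator was significant in the joint model in only about 5% of trials. With no causal order stated, neither model is clearly right alone.

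4. *The cited MacArthur framework handles one mediator at a time.* Naming a framework does not remove confounding by a second mediator that the trial itself plans to study.

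A reader might also quote larger error rates by looking only at the slope in a single-mediator model without the interaction: 17-33%, 40-71% and 54-85% at correlations 0.3, 0.5 and 0.6. Those figures do not describe the plan's rule, which also requires γ1 and includes the interaction. For the same reason a joint-model power of 80-99% cannot be claimed with a 0.25 SD shift, since γ1 alone caps it at about 77%.

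**Conclusion.** The point holds for the interpretation of mechanism and no further. As written, the rule can credit a mediator with no effect of its own on abstinence if arm moves it and it correlates with the active one. Under the main assumptions the chance is about two to six times the zero-correlation rate, depending on correlation and effect size. It is small if the correlation is low, or if arm barely moves the inert mediator. The correlation, shifts, effect sizes and abstinence rate are all assumed.

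The documents do not support a claim that the abstinence or pain comparisons are compromised, nor that the single-mediator models should be discarded. A joint model also leaves unmeasured mediator-outcome confounding untouched. This is worth correcting before analysis but does not threaten the trial's main result.

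**What to change.** In the analysis paragraph under Hypothesis 3.1, keep the single-mediator models and add one pre-specified outcome model for 12-month abstinence containing arm and both mediators, with the arm interactions if these are retained. State in advance how the results will be read:

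- **Distinct pathway:** γ1 is non-zero and the mediator's coefficient holds in the joint model.
- **Not separable:** the mediator passes only in its single-mediator model. Report it as shared with, or upstream of, the other mediator. Do not present it as an independent mechanism, and do not call it refuted.

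The cost is a few sentences and one further model. It needs no measurements beyond those the planned mediation analysis already presupposes. The downsides are the loss of precision from collinearity (about 15% on the standard error at correlation 0.5, more with interactions), and that the joint model shows only the direct part if one mediator acts through the other. Retaining the single-mediator fits covers the second.
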